### **Safety Analyses**

No formal statistical testing of safety data is planned. All safety data will be analyzed descriptively by group. All safety analyses will be based on the FA Set.

## 1.2. Schema

Figure 1: Schematic Overview of the Study

\* Screening and vaccination may be split into 2 visits in consultation with the sponsor or its delegate, for example when a criterion for temporarily delaying study vaccine administration (see Section 5.5., Criteria for Temporarily Delaying Study Vaccine Administration) is met.

\*\* By telephone.

\*\*\* In case any of the criteria for temporarily delaying study vaccine administration (see Section 5.5., Criteria for Temporarily Delaying Study Vaccine Administration) are met at Visit 3 (Day 30), the administration of the second study vaccination needs to be delayed (up to a maximum of 10 days on top of the allowed time window of Visit 3 [ $\pm 7$  days]). The immunogenicity and safety assessments of Visit 3 should still be performed on the actual Day 30 ( $\pm 7$  days).

## 1.3. Schedule of Activities (SoA)

Clinic Visit #	1 a	2 b ☎	3 a	4 b ☎	5 a	6 b ☎	Exit b,c ☎
Visit Timing	Vac 1	Vac 1 + 14 d	Vac 1 + 29 d	Vac 2 + 14 d	Vac 2 + 29 d	Vac 2 + 6 mo	
Visit Day	-8 to 1	15	30	44	59	210	
Visit Window		±2 d	±7 d	±7 d	±7 d	±42 d	
Visit Type	Screening and VACCINATION 1 d	Safety	VACCINATION 2	Safety	Immunogenicity and Safety	Safety	Early exit
Written informed consent e	●						
Inclusion/exclusion criteria	●						
Demographics	●						
Medical history f /prestudy therapies g	●						
Vital signs h incl. body temperature	●		●				
Physical examination	●						
Height and weight	●						
Randomization	●						
Inclusion/exclusion criteria check j			●				
Prevaccination symptoms k	●		●				
Humoral immunogenicity, mL	● 30		● 30		● 30		
Vaccination k	●		●				
30-minute post-vaccination observation l	●		●				
Solicited AE recording m	----- ③ -----		----- ③ -----				④
Unsolicited AE recording n	----- continuous -----						⑤
MAAE and SAE recording	----- continuous -----						●
Concomitant therapies o	----- continuous -----						●
Participant wallet card	----- continuous -----						
Issue participant eDiary p,q	●		●				
Participant eDiary review by site staff q		●	●	●	●		
Approximate daily blood draw, mL	30 r	—	30 r	—	30 r		—
Approximate cumulative blood draw, mL	30	30	60	60	90		—

Footnotes are provided on the next page

AE = adverse event; d = days; ICF = informed consent form; mo = months; MAAE = medically-attended adverse event; SAE = serious adverse event; vac = vaccination

☎ telephone contact or other means of communication; ❶ prevaccination; ❷ pre- and post-vaccination; ❸ solicited local (injection site) and systemic AEs will be collected via participant eDiary from vaccination until 14 days after each vaccination; ❹ if within 14 days of the previous vaccination; ❺ if within 29 days of the previous vaccination

#### Footnotes:

- a. Visits that cannot be conducted in person at the study site may be conducted as home health visit after sponsor approval.
- b. Safety visits and early exit visit will be by telephone.
- c. An early exit visit will be conducted as soon as possible for those participants who are unable to continue participation in the study and withdraw from the study before Day 210, but who do not withdraw consent. Participants who wish to withdraw consent from participation in the study will be offered an early exit visit (prior to formal withdrawal of consent).
- d. Screening and vaccination may be split into 2 visits in consultation with the sponsor or its delegate, for example when a criterion for temporarily delaying study vaccine administration (see Section 5.5. Criteria for Temporarily Delaying Study Vaccine Administration) is met. Every effort should be made for split visits to occur preferably within 3 to 5 days and no later than 10 days, and prevaccination vital signs should be repeated on the day of vaccination if this visit is split.
- e. Signing of the ICF should be done before any study-related activity.
- f. Information about planned surgeries and/or procedures should be reported. Medical history of all participants will be recorded in the eCRF. Participants will be specifically questioned regarding the medical history of UTI. This includes any uncomplicated, complicated, or recurrent UTIs that were diagnosed by a physician (or qualified healthcare provider) and that required antimicrobial therapy. The details will be collected in the eCRF. Note: a history of isolated male accessory gland infections will not be considered as a history of UTI.
- g. Prestudy therapies administered up to 30 days before the first study vaccination must be recorded on Day 1.
- h. Sitting systolic and diastolic blood pressure, heart rate, and respiratory rate after at least 5 minutes rest on Days 1 and 30. At non-vaccination visits, vital signs will be measured if deemed necessary by the investigator.
- i. General physical examination; it is at the investigator's discretion how detailed the examination (which body systems are to be covered) is deemed needed. At any other visit, a targeted (abbreviated and symptom-directed) examination may be performed if deemed necessary by the investigator based on any clinically relevant issues, clinically relevant symptoms, and medical history.
- j. Inclusion Criterion 2 and Exclusion Criteria 2, 4, 5, 6, 9, 10, 11 and 12.
- k. Investigator must check for clinically significant acute illness at the time of vaccination, body temperature  $\geq 38.0^{\circ}\text{C}$  ( $\geq 100.4^{\circ}\text{F}$ ) within 24 hours prior to the planned time of vaccination, an illness which in the judgment of the investigator may interfere with reactogenicity or safety assessments, and whether the participant recently received a medically indicated vaccination. If any of these events occur at the scheduled time for the first vaccination, randomization at a later date within the screening period (allowed window up to 8 days) is permitted. If any of these events occur at the scheduled time for the second vaccination, the vaccination can be delayed up to 10 days on top of the allowed time window of Visit 3 ( $\pm 7$  days). The immunogenicity and safety assessments of Visit 3 should still be performed on the actual Day 30 ( $\pm 7$  days).
- l. After each vaccination, participants will be observed for at least 30 minutes for presence of any acute reactions and solicited events. Any unsolicited AEs, solicited local (injection site) or systemic AEs, and vital signs (systolic and diastolic blood pressure [sitting], heart rate, respiratory rate, and body temperature) will be documented by study-site personnel following this observation period.
- m. Includes the assessment of the severity of solicited AEs during the Visit 2 and Visit 4 phone calls.
- n. Includes the assessment of the severity of unsolicited AEs and the occurrence of special reporting situations during all visits up to 29 days post-vaccination, including the Visit 2 and Visit 4 phone calls.

- o. Concomitant therapies will be collected from the time of first study vaccination through 29 days after the last study vaccination when associated with an AE, and from ICF signature until 6 months after the last study vaccination when associated with an SAE. Concomitant therapies associated with solicited AEs will be collected by the participants in the participant eDiary from the time of study vaccination through 14 days after each vaccination.
- p. Rulers and thermometers will be distributed at Visit 1 and at Visit 3, if applicable.
- q. eDiary entries will be reviewed with the participant by a qualified and delegated study staff member (eg, investigator, sub-investigator, or study nurse). The delegated study staff member grades any signs or symptoms using the toxicity grading scale ([Appendix 5: Toxicity Grading Scale](#)) and will complete their assessment in the relevant sections of the eCRF. The eDiary review and grading of symptoms are done under the oversight of the investigator or a delegated physician.
- r. Aliquots of serum samples collected for immunogenicity tests can be reconverted for participant's safety purposes upon sponsor request.

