
 
To compare seroprotection rates against the 4 influenza vaccine strains after the concomitant administration of ExPEC9V and a HD quadrivalent seasonal influenza vaccine versus the administration of a HD quadrivalent seasonal influenza vaccine alone.
 
	
 
Seroprotection is defined for each of the 4 influenza vaccine strains as HI titer <math>\geq 1:40</math> at 29 days after the administration of a HD quadrivalent seasonal influenza vaccine.
 

 
To assess the safety and reactogenicity of ExPEC9V when administered separately or concomitantly with a HD quadrivalent seasonal influenza vaccine
 
	
 
Solicited local (injection site) and systemic AEs for 14 days post each vaccination.
 
Unsolicited AEs for 29 days post each vaccination.
 
MAAEs collected from administration of the first vaccination until 6 months post last vaccination.
 
SAEs collected from the administration of the first vaccination until 6 months post last vaccination.
 

 
To evaluate the immunogenicity of ExPEC9V when administered separately or concomitantly with a HD quadrivalent seasonal influenza vaccine.
 
	
 
Antibody titers to vaccine O-serotype antigens and EPA as determined by multiplex ECL-based immunoassay on Days 1, 30, and 59.
 

Objectives	Endpoints

 
To further evaluate the immunogenicity of ExPEC9V when administered separately or concomitantly with a HD quadrivalent seasonal influenza vaccine.
 
	
 
Opsonophagocytic antibody titers to vaccine O-serotype antigens as determined by MOPA 29 days after administration of ExPEC9V.
 

 
To evaluate the immunogenicity of ExPEC9V between participants with a history of UTI to those without a UTI history.
 
	
 
Antibody titers to vaccine O-serotype antigens, in participants reporting a history of UTI at enrollment and participants without a UTI history at enrollment, as determined by multiplex ECL-based immunoassay 29 days after administration of ExPEC9V.
 

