### **Visit Windows**

Visit windows are provided in the Schedules of Activities.

The timings of the post-vaccination visits will be determined relative to the actual day of the corresponding vaccination. If a participant misses a vaccination, the post-vaccination visits will be calculated from the imputative vaccination date according to protocol.

Note: In case any of the criteria for temporarily delaying study vaccine administration (see Section 7.1., Discontinuation of Study Vaccination) are met at Visit 3 (Day 30), this visit would need to be split into 2 visits. The administration of the second study vaccination can be delayed up to 10 days on top of the allowed time window of Visit 3 ( $\pm 7$  days). The immunogenicity and safety assessments of Visit 3 should still be performed on the actual Day 30 ( $\pm 7$  days).

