### **8.3. Adverse Events, Serious Adverse Events, Medically-attended Adverse Events, and Other Safety Reporting**

Timely, accurate, and complete reporting and analysis of safety information, including AEs, SAEs, MAAEs, and PQCs, from clinical studies are crucial for the protection of participants, investigators, and the sponsor, and are mandated by regulatory agencies worldwide. The sponsor has established Standard Operating Procedures in conformity with regulatory requirements worldwide to ensure appropriate reporting of safety information; all clinical studies conducted by the sponsor or its affiliates will be conducted in accordance with those procedures.

AEs and MAAEs will be reported by the participant (or, when appropriate, by a caregiver, surrogate, or the participant's legally acceptable representative) for the duration of the study.

Further details on AEs, MAAEs, SAEs, and PQCs can be found in [Appendix 3: Adverse Events, Serious Adverse Events, Medically-attended Adverse Events, Product Quality Complaints, and Other Safety Reporting: Definitions and Procedures for Recording, Evaluating, Follow-up, and Reporting](#).

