#### **All Adverse Events**

AEs and special reporting situations, whether serious or non-serious, that are related to study procedures or that are related to non-investigational sponsor products will be reported from the time a signed and dated ICF is obtained until the end of the study/early withdrawal.

Clinically relevant medical events not meeting the above criteria and occurring between signing of ICF and moment of first vaccination will be collected on the Medical History eCRF page as pre-existing conditions.

Solicited AEs, collected through an eDiary, will be recorded for each vaccination from the time of vaccination until 14 days post-vaccination.

All unsolicited AEs and special reporting situations will be collected for each vaccination from the time of vaccination until 29 days post-vaccination. Unsolicited AEs with the onset date outside the timeframe defined above (>29 days after previous study vaccination), which are ongoing on the day of the subsequent vaccination, should be recorded as such.

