5.6.1.4. Missing Data

Missing data will not be imputed. Participants who do not report an event will be considered as participants without an event. An AE with a missing severity or relationship will be considered as an AE reported but will be considered as not reported for the severity or relationship. For example, an AE with missing severity will be considered as an AE reported for the analysis of any grade but will be considered as not reported for the analysis of at least Grade 3.

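### An in-window Visit 5 can fall up to 7 days before the 29-day unsolicited-AE period after dose 2 ends, and no later scheduled enquiry clearly covers the remaining days

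*Protocol*

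**What the plan says.** Protocol Section 3 sets the secondary safety endpoint as "Unsolicited AEs for 29 days post each vaccination". Protocol Section 8.3.1 makes this a collection rule: "All unsolicited AEs and special reporting situations will be collected for each vaccination from the time of vaccination until 29 days post-vaccination".

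In the Schedule of Activities (Protocol 1.3), Visit 5 is placed 29 days after dose 2 and Visit 6, a telephone call, 6 months after dose 2. The windows for Visits 2 to 6 read "Visit Window ±2 d ±7 d ±7 d ±7 d ±42 d", so Visit 5 has ±7 days and Visit 6 ±42 days. Protocol Section 8 fixes the anchor: "The timings of the post-vaccination visits will be determined relative to the actual day of the corresponding vaccination".

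Footnote n describes unsolicited-AE recording as follows: "Includes the assessment of the severity of unsolicited AEs and the occurrence of special reporting situations during all visits up to 29 days post-vaccination". It names the Visit 2 and Visit 4 calls among those visits. The early-exit column carries a similar condition: unsolicited AEs are recorded there only if the exit contact is within 29 days of the last vaccination. Section 8.3 also states "AEs and MAAEs will be reported by the participant", with that route open for the whole study.

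In the SAP, Table 4 ends the Post-dose 2 period at the later of day 29 and the completed visit, absent early discontinuation or data cut-off. Section 5.6 uses all participants in the phase as the denominator for unsolicited AEs. Section 5.6.1.4 adds: "Participants who do not report an event will be considered as participants without an event".

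**The concern.** The collection period is defined by when an event starts, whereas the scheduled enquiry is defined by when the contact takes place. The two agree only if the last enquiry is on or after day 29. After dose 2 a fully compliant Visit 5 can be earlier, and the following contact is months away and outside the wording of footnote n. The eDiary does not help, because it holds solicited events only, for 14 days.

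The gap matters most after dose 2. The same ±7-day tolerance applies to Visit 3 after dose 1, but Visits 4 and 5 follow and ask again. Nothing comparable follows Visit 5. Dose 2 is also the Control group's only ExPEC9V dose, so it supplies the separate-administration half of the safety objective. Events that are not reported would lower that group's ExPEC9V-alone percentages, and the SAP gives the reader no means of seeing by how much.

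**Working it through.** **Inputs.** Visit 5 target of 29 days after dose 2, ±7 days (Schedule of Activities); dose 2 on Day 30 and Visit 6 on Day 210, ±42 days (same table); SAP Table 5 window [23, 37] with dose 2 as Day 1.

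**1. Reproduce the plan's own window.** Day 29 after dose 2 is relative day 30. 30 − 7 = 23 and 30 + 7 = 37, which matches SAP Table 5. In days after dose 2 this is 22 to 36.

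**2. Days left without a clear scheduled enquiry.** Days = max(0, 29 − Visit 5 day). A visit on day 28 leaves 1 day; a visit on day 22 leaves 7. The largest share is 7/29 = 24.1%.

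**3. Time to the next contact.** Visit 6 is nominally 210 − 30 = 180 days after dose 2. The window gives 180 − 42 = 138 days (about 4.5 months) to 180 + 42 = 222 days (about 7.3 months). From a day-22 Visit 5 the gap is 158 days nominally, ranging from 116 to 200.

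**4. Average over participants.** The documents give no attendance distribution, so two are assumed over the 15 possible days.
- Uniform: share early = 7/15 = 47%. Mean days = (7+6+5+4+3+2+1)/15 = 28/15 = 1.87, and 1.87/29 = 6.4%.
- Triangular, peaking on day 29 (weights 1, 2, …, 8, …, 2, 1; sum 64): share early = 28/64 = 44%. Mean days = (7×1 + 6×2 + 5×3 + 4×4 + 3×5 + 2×6 + 1×7)/64 = 84/64 = 1.31, and 1.31/29 = 4.5%.

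**5. From days to percentages (illustration only).** Assume a constant hazard and that no event after Visit 5 is ever reported. With true 29-day incidence I, the incidence observed for a visit on day d < 29 is 1 − (1 − I)^(d/29).

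| True I | All seen on day 22 | Uniform over days 22 to 36 |
|---|---|---|
| 5% | 3.8% | 4.7% |
| 10% | 7.7% | 9.4% |
| 20% | 15.6% | 18.8% |
| 30% | 23.7% | 28.3% |

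The values of I are assumptions, since the documents give no unsolicited-AE rate. Both assumptions about the data push the loss upward if later reporting occurs or if events cluster soon after vaccination.

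**The case against.** The strongest reply is that the protocol already requires the data. Section 8.3.1 mandates collection to day 29, so an event starting on day 26 must be recorded whenever the site learns of it. Footnote n is worded inclusively and need not be read as a prohibition. Participants may report AEs throughout, carry a card with a 24-hour number, and may have unscheduled visits. Section 8.3.2 prefers open-ended questioning, so the Visit 6 call could elicit such events. The schedule marks unsolicited-AE recording as continuous, and the extracted table does not show which columns that line spans.

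This reply stands against a stronger reading that a reader might infer, namely that the 29-day endpoint is not delivered or that these events are never asked about. The documents do not support that. They do not, however, name any contact at which early attenders are to be asked about the missing days. A requirement to collect, without a scheduled question, leaves capture to volunteering or to recall months later.

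The exposed set is also narrow. SAEs, MAAEs and AEs leading to discontinuation are collected to the last study procedure, and procedure-related AEs to the end of the study. Solicited reactions to the related ExPEC4V and ExPEC10V vaccines began mostly in the first days, with late-onset ones from about the end of the first week. That suggests few vaccine reactions start on days 23 to 29, although those data concern solicited events. Finally, safety is descriptive and the window is the same in both groups. These points limit the size of the problem without closing the gap.

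**Conclusion.** The point holds as a modest, avoidable weakness in ascertainment. For participants whose in-window Visit 5 falls 22 to 28 days after dose 2, no scheduled enquiry clearly covers the last 1 to 7 days of the unsolicited-AE period. Non-serious, non-medically-attended AEs that start then and do not lead to discontinuation rest on spontaneous report, and the SAP counts non-report as absence over at least 29 days for everyone. Any error is toward under-counting.

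The 24% ceiling for one participant follows from the documents. The 4.5% to 6.4% averages rest on assumed attendance and measure days of follow-up, so they should not be read as the share of events lost. It would also go too far to infer a built-in imbalance between groups within the post-dose 2 period, because the schedule is the same for both. The consequence differs only because dose 2 is ExPEC9V in one group and placebo in the other. No hypothesis test, primary endpoint or sample size is touched.

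**What to change.** **Protocol.** Reword footnote n and the Visit 6 procedures so that they refer to the onset date of the AE. If Visit 5 took place before day 29 after dose 2, the next contact should ask for and record any unsolicited AE with onset from Visit 5 through day 29. A brief call soon after day 29, for early attenders only, is optional and gives better recall. The Visit 5 blood-draw window can stay as it is.

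**SAP Section 5.6.** Report by group how many participants had their last unsolicited-AE enquiry before day 29 after dose 2. Repeat the Post-dose 2 unsolicited-AE summary in those ascertained through day 29. Both need only visit dates that are already collected, so this part can be done even if Visit 5 is complete.

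**Cost.** One sentence in the schedule, one conditional question at an existing call, and one extra table. The downside is longer recall if the question is asked only at Visit 6, or a short extra call. Answers obtained at Visit 6 would arrive after the primary analysis, and SAP Section 5.8 mentions only MAAE and SAE data for the final analysis, so that section should state that the Post-dose 2 unsolicited-AE summary is updated then.

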## 2. INTRODUCTION

ExPEC9V (primary compound number: VAC52416) is a 9-valent vaccine candidate in development for active immunization for the prevention of invasive extraintestinal pathogenic *Escherichia coli* (ExPEC) disease (IED) in adults 60 years of age and older. ExPEC9V consists of the O-antigen polysaccharides (PSs) of the ExPEC serotypes O1A, O2, O4, O6A, O15, O16, O18A, O25B, and O75 separately bioconjugated to the carrier protein, a genetically detoxified form of exotoxin A derived from *Pseudomonas aeruginosa* (EPA).

For the most comprehensive nonclinical and clinical information regarding VAC52416 (JNJ-78901563), refer to the latest version of the IB for VAC52416 (JNJ-78901563).

The term “study vaccination” throughout the protocol, refers to ExPEC9V, placebo, or the high-dose (HD) quadrivalent seasonal influenza vaccine as defined in Section 6.1., Study Vaccinations Administered.

The term “sponsor” used throughout this document refers to the entities listed in the Contact Information page(s), which will be provided as a separate document.

The non-inferiority criteria used in this study are based on guidance from regulatory authorities (for details, refer to Section 9.2., Sample Size Determination).

### 2.1. Study Rationale

ExPEC is a leading and increasing cause of bacteremia/bloodstream infections worldwide and comprises 17% to 37% of blood isolates (De Kraker 2013, Johnson 2003, Laupland 2014). In the US, the overall annual incidence of ExPEC bloodstream infections in adults ranges between 30 and 50/100,000 person-years (Laupland 2014, Williamson 2013). In Europe, the number of cases of ExPEC bacteremia annually increased by 8.1% between 2002 and 2008 (De Kraker 2013).

IED is defined as an acute illness consistent with systemic bacterial infection, which is microbiologically confirmed either by the isolation and identification of *E. coli* from blood or any other sterile body sites, or by the isolation and identification of *E. coli* from urine in a patient with urosepsis and no other identifiable source of infection. Although IED affects all ages, adults aged  $\geq 60$  years have an increased risk of developing IED, including bacteremia and sepsis. In a retrospective population-based study in the US from 1998 to 2007, the incidence of *E. coli* bloodstream infections was shown to increase markedly with age from 60 years onwards. The incidence rates in adults aged  $\geq 60$  years were estimated to be between 136 to 152/100,000 person-years; while by age stratum, incidence rates were estimated at 100/100,000 person-years in adults aged 60 to 79 years, and 300/100,000 person-years in adults aged  $\geq 80$  years. The urinary tract was found to be the most common primary source of infection (79.8%) (Al-Hasan 2009a, 2009b).

ExPEC9V, which is currently in Phase 3 development for prevention of IED, is targeting the population aged  $\geq 60$  years in which seasonal influenza vaccination is also frequently recommended in different regions. To be able to deploy ExPEC9V as medically appropriate, data needs to be accrued that would allow concurrent administration of ExPEC9V and other vaccination interventions (such as influenza vaccination) that regularly target the population of interest. The current study will examine the immunogenicity and safety of ExPEC9V co-administered with a

HD quadrivalent seasonal influenza vaccine (co-administration [CoAd] group) compared to administration of each vaccine separately (Control group). The aim is to provide an indication of whether these vaccines can be administered concomitantly.

The present study also aims to include participants (aged  $\geq 65$  years) with and without a previous history of UTI to allow a comparison of vaccine-elicited immunogenicity between the 2 populations (ie, with a previous UTI history versus without a previous UTI history). Participants with a previous UTI history, particularly if some of the UTIs were attributable to *E.coli* infection, have been observed to elaborate higher baseline immune responses targeting *E.coli* O-antigens, as shown in the VAC52416BAC1001 study Cohort 2 (see Section 2.2., Background). This observation needs to be further investigated through a comparison of immunogenicity elicited by the vaccine for the 2 aforementioned populations.

